### 3.0 OBJECTIVES

#### **Primary Study Objectives:**

- 1) Evaluate the effectiveness of doxycycline post-exposure prophylaxis (dPEP) to reduce STI infections in HIV-uninfected Kenyan women taking HIV PrEP.
- 2) Assess the safety, tolerability, and acceptability of dPEP.
- 3) Assess adherence to dPEP.
- 4) Investigate the impact of dPEP on development of tetracycline resistance in *N. gonorrhoeae* and *C. trachomatis*.
- 5) Measure the cost of dPEP and estimate the cost per case averted, budget impact, and affordability.

#### **Secondary Study Objectives:**

- 1) Investigate the impact of dPEP on development molecular markers of tetracycline resistance (tetR) in *Mycoplasma genitalium* and nasopharyngeal carriers of *S. aureus* and other commensal organisms from swabs from all participants, stored for future evaluation.
- 2) Assess the effect of dPEP on the vaginal microbiome through quantitative polymerase chain reaction (PCR) and *Lactobacillus* and other flora resistance to doxycycline from vaginal swabs from all participants, stored for future evaluation.

- 3) Assess the effect of indole producing organisms in the vaginal microbiome on the effect of dPEP from quarterly vaginal swabs from all participants, stored for future evaluation.

## 4.0 SELECTION AND ENROLLMENT OF PARTICIPANTS

### **Inclusion criteria**

- 1) Willing and able to give written informed consent
- 2) Age  $\geq 18$  years and 30 years old
- 3) Female sex at birth
- 4) HIV-seronegative, according to national HIV testing algorithm
- 5) Has a current prescription for PrEP, according to the national guidelines of Kenya.

### **Exclusion criteria**

- 1) Pregnant
- 2) Breastfeeding a child
- 3) Allergy to tetracycline class
- 4) Current medications which may impact doxycycline metabolism or that are contraindicated with doxycycline, as per the prescribing information. These include systemic retinoids, barbiturates, carbamazepine, phenytoin, and warfarin.
- 5) Recent use of prolonged (more than 14 day course) antibiotics in the month prior to enrollment
- 6) Active, clinically significant medical or psychiatric conditions that would interfere with study participation, at the discretion of the site investigator or designee.

### **Recruitment**

We will be recruiting from clinics providing PrEP in Kisumu. The experienced community outreach team at the study site in Kisumu employs community-based mobilization strategies, including engaging community health volunteers, gate keepers, peer to peer mobilization, youth peer providers and ambassador models, use of printed and electronic IEC materials, social media (WhatsApp and Facebook), radio talk shows in English, *Kiswahili*, and the local *DhoLuo* dialects, active participation in local social events for information sharing, and partnering with learning institutions to give health talks and to provide study related information. Careful attention to confidentiality is made in the recruitment process and potential participants are never approached individually in group settings or public messaging. Recruitment messaging is screened for cultural and community acceptability to reduce risk of stigma for study participants. Potential participants who are not interested in the study or do not meet study eligibility criteria, may be notified of alternative studies that they may be eligible for, or provided information about where to access standard of care for HIV prevention and STI services.

## 5.0 STUDY TREATMENT

### **Study product**

Generic immediate release doxycycline hydiate 100 mg capsules will be provided by the study to participants randomized to open-label dPEP. Doxycycline hydiate is a standard formulation of doxycycline that is widely available internationally and FDA approved for the treatment of a number of infectious conditions. Doxycycline hydiate will be purchased from a quality-controlled supplier in Kenya and with consultation by the Kenya National AIDS and STI Control Programme. To ensure consistency and quality of the doxycycline, we will use the same formulation of drug for the duration of the trial and work with suppliers able to provide evidence of following good manufacturing practices.

### **Safety of doxycycline**

Doxycycline is an antibiotic that can be used for prolonged periods of several months in the treatment of acne or in the prevention of malaria. The tolerance of repeated-dose of doxycycline in this 12-month study should therefore be acceptable.

The possible side effects of doxycycline are

- Gastrointestinal: nausea, diarrhea, epigastric pain, and candidiasis
- Esophageal disorders: dysphagia, pill esophagitis, and rarely esophageal ulceration. Risk for esophageal irritation can be reduced by taking doxycycline capsules at least one hour before bedtime (to avoid being lying down with doxycycline intake) at a meal with a glass of water (100 ml).
- Skin reactions including maculopapular, erythematous, and photosensitivity skin reactions.

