#### **Clinical study care**

**Review of current medications:** All participants will have current medications reviewed at screening for possible drug interaction with doxycycline. At subsequent quarterly visits, participants randomized to dPEP will have current medications reviewed and any new medications will be assessed for possible drug interactions.

**STI symptom screen:** Participants will be asked about current STI symptoms including vaginal discomfort, dysuria, rash, vaginal discharge, rectal pain, pelvic pain, and genital lesions.

**General symptom assessment:** At each visit, participants in both study arms will be asked about possible doxycycline side effects, including esophagitis, rash, gastrointestinal symptoms, photosensitivity, headache, and vaginal yeast infection. Control arm participants will be asked about these symptoms to establish a comparator for non-specific symptoms which can occur in the absence of doxycycline.

**Risk reduction counseling:** At each visit, staff will counsel participants about risk reduction and HIV and STI prevention and will receive condoms.

**Pill count and dPEP adherence assessment:** Participants assigned to dPEP will be asked to bring their doxycycline blister packs in at each visit for a pill count. While completing the timeline follow-back calendar to record sexual exposures will be asked when dPEP was taken and if each sex act were covered by dPEP in the past 3 months.

**PrEP adherence assessment and counseling:** All participants will receive quarterly PrEP adherence assessment (Likert scale) and adherence counseling.

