### *Specific Management of Toxicities Related to Study-Provided Drugs*

#### Possible intracranial hypertension (IH)

Participants taking doxycycline who report new or worsening headaches, visual changes or vision loss should have doxycycline temporarily discontinued and evaluated for IH, including a fundoscopic exam to look for papilledema. If IH is ruled out or an alternate etiology identified, doxycycline may be restarted, at the discretion of the site investigator.

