#### Allergic reactions

Doxycycline should be discontinued permanently if an allergic reaction is suspected. These participants will remain on study, off study treatment and have all evaluations performed per current clinical guidelines.

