### **Risks/Benefits**

Participants may experience pain or discomfort during blood draws pelvic exams, and rectal and nasal swab collection. They may be embarrassed or worried about the STI and HIV testing conducted during the study. Participants may also have some anxiety or worry about providing a hair sample, though the technique is optimized to minimize visible hair removal. Study questionnaires asking information about sexual behavior or partners may also make the participant uncomfortable or embarrassed. All study staff are trained to provide professional care in both clinical sample collection and counseling and administering study questionnaires. Counseling will be available to participants who feel they would benefit based on their experiences in the study.

Weekly SMS will be received outside of the study clinic and thus study staff cannot guarantee that someone other than the participant will see the message. The SMS will be coded so that if another person sees the message, it will not indicate the nature of the question or reveal that it is part of a research study. The participant may respond to the message at anytime she feels comfortable to do so, i.e. it does not require an immediate response. Additionally, if ever she would like to stop receiving the weekly SMS, she may request this from the study staff and she will be removed from the list of participants receiving the SMS.

For women assigned to the dPEP group, there are known side effects, as listed in protocol section 5.0. Participants will be counseled on the side effects and ways to take the medication in order to minimize the impact of any side effects. Participants will be encouraged to come to the study clinic if they have any concerns about the medication or side effects they are experiencing.

Study staff will make every effort to protect participants' privacy and confidentiality. It is possible that participants' involvement in the study could become known to others, and that social harms may result (i.e., because participants could become known as participating in a trial involving sexually active women or persons using PrEP). For example, participants could be treated unfairly or discriminated against, or could have problems being accepted by their families and/or communities. It is possible that participants may have problems with their partner or experience intimate partner violence. Counseling and referrals will be available, if needed.

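### The side-effect list used to counsel dPEP-arm women names none of the symptoms that trigger the intracranial hypertension rule, and the visit symptom list names headache but no visual symptom

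*Protocol*

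**What the plan says.** Protocol section 5.0 (Safety of doxycycline) opens its list with "The possible side effects of doxycycline are" and gives three entries: "Gastrointestinal: nausea, diarrhea, epigastric pain, and candidiasis"; "Esophageal disorders: dysphagia, pill esophagitis, and rarely esophageal ulceration"; and "Skin reactions including maculopapular, erythematous, and photosensitivity skin reactions". Section 12.0 (Risks/Benefits) refers back to it: "For women assigned to the dPEP group, there are known side effects, as listed in protocol section 5.0". The next sentence there says that participants are counseled on these effects. The dispensing text in section 5.0 also promises dPEP-arm women advice on side effects and how to manage them, but gives no second list.

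Section 8.0 has a specific rule for possible intracranial hypertension (IH). It applies to "Participants taking doxycycline who report new or worsening headaches, visual changes or vision loss", and it leads to a temporary stop of doxycycline and an evaluation. The allergy rule reads "Doxycycline should be discontinued permanently if an allergic reaction is suspected". Skin erythema and fixed drug eruption have rules of their own.

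At visits, women in both arms are "asked about possible doxycycline side effects, including esophagitis, rash, gastrointestinal symptoms, photosensitivity, headache, and vaginal yeast infection" (Clinical study care, General symptom assessment). The schedule of procedures places this assessment at Months 0, 3, 6, 9 and 12. SAP 8.3 tabulates the collected symptoms for each arm. SAP 2.2.3 describes the same assessment by naming nausea, pill esophagitis and photosensitivity.

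**The concern.** The IH rule is driven by report. A report reaches the clinician in one of two ways: the woman is asked, or she volunteers it. The list tied to counseling supports volunteering, and the visit symptom list supports asking. If a symptom that triggers the rule is on neither list, the protocol recognizes a toxicity in one section without giving the rule its input in the others.

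There is also a data side. Safety is a primary objective. Apart from serious adverse events, the protocol records an event only if the investigator attributes it to doxycycline, and SAP 2.2.3 assesses related events in the dPEP arm only. The symptom assessment is therefore the main source for comparing non-serious symptoms by arm. The protocol says that control women are asked the same questions to supply a background level for non-specific symptoms. A symptom that is not on the form has no such background level.

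**Working it through.** No arithmetic applies, because the plan states no figure on this point. The check sets the section 8.0 items beside the two lists.

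| Item in section 8.0 | Section 5.0 list (counseling) | General symptom assessment (visits) |
|---|---|---|
| Headache | not named | named |
| Visual changes or loss of vision | not named | not named |
| IH as a named risk | not named | not named |
| Allergic reaction | not named; maculopapular and erythematous skin reactions are | not named; rash is |
| Fixed drug eruption | not named; skin reactions in general are | not named; rash is |
| Skin erythema | covered by erythematous and photosensitivity reactions | covered by rash and photosensitivity |

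In the supplied text, visual symptoms appear only in the IH rule. Headache appears only there and in the general symptom assessment. Allergy appears only in the exclusion criteria and in the allergy rule.

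Next, follow each route to the IH rule.

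1. *Scheduled visit, headache present.* The woman is asked about headache. The rule's symptoms are alternatives, so headache alone can start it. There is no gap.
2. *Scheduled visit, visual symptom without headache.* No named question covers it. The rule depends on the woman raising it, or on the form containing more than the protocol names.
3. *Between visits.* The protocol provides interim visits for possible doxycycline adverse events and invites women with concerns to return. The route is open, but using it requires a woman to connect the symptom with the drug. The list tied to counseling does not make that connection for headache or for vision.

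Month 0 is the randomization visit, before any dPEP is taken. The assessments under treatment are therefore those at Months 3, 6, 9 and 12.

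For the by-arm data, headache is collected in both arms and falls under SAP 8.3, although SAP 2.2.3 does not name it. Serious adverse events are recorded in both arms whatever their cause (SAP 3.5) and tabulated by arm (SAP 8.1.2). What is missing is a by-arm row for visual symptoms.

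**The case against.** The best defense is that the three texts do different jobs. One is a summary of known effects, one is a screening question, and one is a set of management rules. None of them denies another. The wording of the visit list is open-ended, so the form may ask more than the protocol names. The consent pages were removed from the reviewed text, and no counseling script or symptom form is supplied, so IH may well be mentioned there. The promise of advice on managing side effects could also be read as reaching into section 8.0. Women are encouraged more than once to come in with any concern.

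Most of this stands, and it limits the point. It also rules out several stronger readings that a reader might infer:

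- *Women are not warned of IH at all.* The documents cannot show this, because the consent form is not available.
- *A symptom could go unnoticed for a whole quarter under dosing.* This overlooks the interim visits and the encouragement to return.
- *The safety objective has no comparison for this toxicity.* Headache and serious adverse events are both compared by arm.
- *A fixed share of the section 8.0 toxicities is missing from section 5.0.* The count depends on the standard. By literal name, three of the four are absent (IH, fixed drug eruption and allergic reaction). If skin signs count as cover, only IH is wholly absent.
- *The allergy rule fails in the same way.* That rule turns on suspicion, not on report. Its skin signs are listed and asked about, and known tetracycline allergy is an exclusion.

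The defense does not remove the mismatch. The section 5.0 list, unlike the visit list, has no open-ended wording for the list as a whole, and section 12.0 points to it by number as the place where the known side effects are set out.

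**Conclusion.** The lists do not match the IH rule and should be reconciled. The gap has two parts: visual symptoms without headache at scheduled visits, and recognition of IH symptoms between visits. Allergic reaction and fixed drug eruption are secondary, because their skin signs are partly covered. The size cannot be put as a number, since the documents give no frequency for IH or for its symptoms. No efficacy result or power figure is touched.

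The conclusion rests on two assumptions: that counseling follows section 5.0, as section 12.0 indicates, and that the symptom form contains the items the protocol names and no visual item. If the consent form or the symptom form already covers vision, the point reduces to aligning the protocol wording. Nothing here bears on whether the management rules are right.

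**What to change.** Reconcile the section 5.0 list, the general symptom assessment and the Risks/Benefits reference with section 8.0, as follows:

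- Name the IH symptoms in the section 5.0 list and, as a secondary matter, allergic reaction and fixed drug eruption. Check that the consent form agrees.
- Add a visual-change item beside headache on the symptom form used in both arms.
- Tabulate that item by arm under SAP 8.3, and bring the description in SAP 2.2.3 into line with the items actually collected.

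The cost is a wording change in the protocol and SAP and one question on a form already given to both arms. The downside is a few more non-specific reports to evaluate. The section 8.0 rules themselves do not change.

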### **Doxycycline dispensing and administration**

Doxycycline will be dispensed at each 3 month visit or in shorter intervals per patient preference, with additional dispensation as needed to replace lost medication or provide additional medication when needed. Capsules should be stored at room temperature (59-86° F) to the extent feasible. Participants will be instructed to take 2 pills of 100 mg doxycycline as soon as possible after condomless sexual contact, ideally within 24 hours but no later than 72 hours after sex. Participants will be instructed to take a maximum of 200 mg in a 24 hour period. For participants reporting sexual encounters on consecutive days, 200 mg of doxycycline will be recommended to be taken until within 24 (and up to 72) hours after the last sexual encounter. Study staff will instruct participants on procedures for replacement of lost medication. Doxycycline may be taken on an empty stomach or with food, and it is advised to take with a large glass of water and to take at least 60 minutes before bed to reduce risk of esophageal irritation. All participants randomized to dPEP will be advised on potential side effects and their management.

### **Concomitant Medications**

Participants randomized to dPEP should report current and new medications to the study team to ensure no concern for drug interactions with doxycycline. The prescribing information for doxycycline hydiate should be reviewed to ensure no potential for drug interactions. Medications that interact with doxycycline include barbiturates, carbamazepine, phenytoin, methoxyflurane, acitretin, isotretinoin, and warfarin. Additionally, medications that interact with doxycycline when taken at the same time include medications that contain cations (iron, aluminum, calcium, or magnesium) and ideally should be separated 2 hours before or after doxycycline.

### **HIV pre-exposure prophylaxis (PrEP), STI treatment, and contraceptives**

PrEP, STI treatment, and contraceptives will be provided by the study and will be accessible through the study clinic or local MOH following the standard of care. All participants diagnosed with an STI will return to the research clinic for treatment, using WHO/Kenya standard therapies, avoiding doxycycline options (i.e. azithromycin, ceftritriaxone, penicillin G benzathine, and metronidazole as needed by pathogen diagnosed) and a second visit two weeks following completion of STI treatment will be done for test of cure; this mitigates potential risk to participants and the community if resistance is selected. The study site will provide contraceptives and PrEP.

## 6.0 STUDY PROCEDURES

	Study Visit Month	S	0	3	6	9	12
Study coordination							
Obtain informed consent Screen for inclusion/exclusion Randomization Collect updated contact information Reimbursement	Obtain informed consent	X					
	Screen for inclusion/exclusion	X	X				
	Randomization		X				
	Collect updated contact information	X	X	X	X	X	X
	Reimbursement	X	X	X	X	X	X
Questionnaires							
Demographic information Behavioral questionnaire HIV risk perception Social Harms and IPV Sexual behavior and exposure history PrEP adherence dPEP adherence (timeline follow-back calendar) Fertility intention Quality of Life	Demographic information	X	X				
	Behavioral questionnaire		X		X		X
	HIV risk perception	X	X	X	X	X	X
	Social Harms and IPV	X	X	X	X	X	X
	Sexual behavior and exposure history	X	X	X	X	X	X
	PrEP adherence	X	X	X	X	X	X
	dPEP adherence (timeline follow-back calendar)			X a	X a	X a	X a
	Fertility intention	X	X	X	X	X	X
	Quality of Life	X	X	X	X	X	X
Clinical Study Care							
Medication review General symptom assessment WHO pregnancy checklist STI symptom assessment Supply condoms Contraception counseling and provision/referral Risk reduction counseling dPEP pill count and refill	Medication review	X	X	X	X	X	X
	General symptom assessment		X	X	X	X	X
	WHO pregnancy checklist	X		X	X	X	X
	STI symptom assessment	X	X	X	X	X	X
	Supply condoms	X	X	X	X	X	X
	Contraception counseling and provision/referral	X	X	X	X	X	X
	Risk reduction counseling	X	X	X	X	X	X
	dPEP pill count and refill			X a	X a	X a	X a
Sample collection							
HIV testing (rapid test) Urine pregnancy testing (rapid test) Syphilis testing (serum RPR) Creatinine (serum) CT/NG testing and resistance (endocervical swabs) c Hair PrEP and doxycycline drug levels Trichomonas screening (vaginal swab)	HIV testing (rapid test)	X		X	X	X	X
	Urine pregnancy testing (rapid test)	X b	X	X b	X b	X b	X b
	Syphilis testing (serum RPR)		X	X	X	X	X
	Creatinine (serum)	X b					
	CT/NG testing and resistance (endocervical swabs) c	X	X	X	X	X	X
	Hair PrEP and doxycycline drug levels		X	X	X	X	X
	Trichomonas screening (vaginal swab)		X	X	X	X	X
Archive							
Microbiome testing (vaginal swab) BV testing (vaginal swab) M. genitalium screening and resistance (endocervical swab) Pharyngeal microbiome and resistance (pharyngeal swab) Rectal microbiome and resistance (rectal swab) Rectal CT screening (rectal swab) HSV-2 testing (serum) Y chromosome DNA testing (vaginal swab) S. aureus resistance screening (nasal swab)	Microbiome testing (vaginal swab)		X	X	X	X	X
	BV testing (vaginal swab)	X	X	X	X	X	X
	M. genitalium screening and resistance (endocervical swab)	X	X	X	X	X	X
	Pharyngeal microbiome and resistance (pharyngeal swab)	X					X
	Rectal microbiome and resistance (rectal swab)						X
	Rectal CT screening (rectal swab)						X
	HSV-2 testing (serum)	X					X
	Y chromosome DNA testing (vaginal swab)	X	X	X	X	X	X
	S. aureus resistance screening (nasal swab)	X	X	X	X	X	X

S = screening visit

aintervention arm only

bif clinically indicated

cParticipants diagnosed with an STI will return 2 weeks following treatment for test of cure

## Study visits

Figure 1. Study visit protocol

Specific study procedures are detailed in Table 6.0. Visits will take place at enrollment and quarterly thereafter, up to 12 months; we will conduct tracing in the case of missed visits to ensure high retention. Interim visits may take place if participants present for diagnosis and treatment of STI, 2 weeks following treatment of STI for test of cure, for subgroup of participants completing in-depth interviews or focus group discussions, or for evaluation of possible doxycycline associated adverse events. All participants will receive quarterly visits for standard of care prevention services and collection of clinical and behavioral data, for a total of 12 months of follow-up. We will use electronic data capture (CommCare or REDCap).

